3.2.4. Rationale for Pharmacodynamic and Biomarker Assessments

Peripheral blood and serum samples will be collected pre- and post-SBT777101 infusion as outlined in the SoA (Appendix A and Appendix B) to evaluate changes in systemic markers of inflammation, including measurements of cytokines, biochemical markers of inflammation and immunophenotyping of circulation cells, including both drug product and cells from subjects. Cytokine levels will be collected frequently over the first month following infusion to permit a thorough evaluation of SBT777101 dosing on inflammation and to aid understanding of the clinical and pathophysiologic impact of CAR T_{reg} cell therapy administration. Samples will be collected out to one year to permit evaluation of the longer-term effects of SBT777101 on PD biomarkers.

3.2.5. Rationale for Synovial Biopsy and Synovial Fluid Assessments

A synovial biopsy will be collected to inform on synovial pathotype and presence of citrullinated protein in the synovial tissue and/or fluid prior to dosing with SBT777101. Additional analyses will be performed on the biopsy sample and synovial fluid to compare pre- and post-treatment levels of citrullinated proteins and other inflammatory biomarkers. The presence of SBT777101 cells within the synovium will also be evaluated at the post-dose time point to determine the extent of CAR T_{reg} trafficking and persistence.

3.3. Dose Escalation Rules

Determination of dosing within a cohort will be overseen by the SMC. Dosing may be temporarily withheld, modified (expansion of cohort size from three to six subjects) or stopped (with no further subject enrollment into the cohort) if any event or series of events occurs that suggests that there is a significant safety risk to subjects, or a clinically significant pattern of toxicity occurs in several subjects.

Dose-Limiting Toxicity Definition

A dose-limiting toxicity (DLT) is defined as any treatment-emergent CTCAE \geq Grade 3 AE considered related to study drug, except Grade 3 infusion reactions that are rapidly reversible with supportive care and that do not recur following re-initiation of the study drug infusion.

If 1 of the first 3 subjects experiences a DLT during the first 28 days after SBT777101 administration, an additional three subjects will be enrolled into the cohort, for a total of 6 subjects. Subjects who discontinue from the study prior to Week 4 for reasons unrelated to study treatment will be considered non-evaluable for dose escalation decisions and will be replaced with another subject at that same dose (see Section 7.4.3).

If 0 of 3 or \leq 1 of 6 subjects experience a DLT during the 28-day DLT evaluation period, and cumulative safety data support tolerability of the dose level as determined by the SMC, escalation to the next higher dose level will be initiated. If \geq 2 subjects in a cohort experience a DLT during the first 28 days or if cumulative safety data suggest an overall unacceptable toxicity profile, dose escalation will be discontinued and either the prior dose level will be considered the maximum tolerated dose (MTD) or an intermediate dose level will be evaluated.

In addition, dose escalation will be temporarily halted if any of the following occur:

- One subject in a cohort experiences a potentially life-threatening AE considered related to study drug
- Two or more subjects experience similar SAEs considered related to study drug

The SMC review of safety data will serve as the basis on which the Sponsor will determine whether dosing can be resumed. Further details may be found in the SMC Charter.

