3.1.1. Overall Study Design

This is a Phase 1, open-label, study to evaluate the safety, tolerability, PK, PD, and preliminary clinical activity of single ascending doses of SBT777101 in patients with active RA.

Following screening, eligible subjects will undergo apheresis, and SBT777101 drug product will be manufactured for each subject. Each subject will receive a single dose of SBT777101 intravenously (IV) on study Day 1. Subject safety will be monitored acutely post dosing and throughout the study for 1 year. After one year and due to the use of lentivirus vector in SBT777101, all subjects will be encouraged to participate in a long-term safety follow-up (observational) study that will be conducted under a separate protocol in accordance with current FDA guidance.

The overall study design is displayed in Figure 1. A schedule of assessments (SoA) is provided in Appendix A and Appendix B.

Figure 1: Study Design

Dose Escalation Cohorts

The study will be open-label and employ a "3+3 Dose Escalation" design. Initially three eligible subjects will be evaluated in each cohort, enrolled for a safety monitoring period at least 14 days apart. Subjects will be monitored for dose limiting toxicities (DLTs) for at least 28 days following enrollment of the third or sixth subject.

- If a DLT is not seen in the first three subjects, then escalation to the next dose level may occur.
- If a DLT is seen in 1 of the first 3 subjects in any dose cohort, the cohort size will be expanded to six subjects. These additional subjects will be dosed at least 14 days apart and have a safety monitoring period of at least 28 days.
- If more than one DLT occurs in ≤6 subjects in a dose cohort, dose escalation will not occur, and this dose level will be identified as the non-tolerated dose. Otherwise, dose escalation may occur.

See Section 3.3 for definitions of DLTs and details of dose escalation rules.

Additional subjects may be screened and undergo apheresis at risk prior to the previous subject within a dose escalation cohort being dosed or completing their post dose safety monitoring period. These additional subjects will not receive treatment with SBT777101 until the safety monitoring period has been completed for the prior subject.

Dose escalation will be overseen by the study Safety Monitoring Committee (SMC; see Section 3.3).

Backfill Cohorts

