7.4.3. Subject Replacement

Subjects in dose escalation cohorts who have been dosed with SBT777101 and withdraw for reasons other than toxicity or are lost to follow-up before completing the safety evaluation period (up to study Day 28) will be replaced.

Additionally, a replacement subject may be enrolled in the study at the discretion of the Sponsor if one or more enrolled subjects are not fully evaluable for purposes of complete safety, PK or PD determination. These replacement subjects may be enrolled while the cohort is still ongoing or concurrently with subsequent cohorts.

Subjects in backfill cohorts that withdraw from the study will not be replaced.

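### Read literally, the DLT evaluability rule lets an observed DLT drop out of the 3+3 count; by implication it may also keep an early toxicity leaver in the count as DLT-free

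*Protocol*

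**What the plan says.** Section 3.3 of the protocol ties evaluability to the reason for leaving: "Subjects who discontinue from the study prior to Week 4 for reasons unrelated to study treatment will be considered non-evaluable for dose escalation decisions". These subjects are replaced at the same dose, with a cross-reference to section 7.4.3.

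Section 7.4.3, repeated in the synopsis under replacement of participants, covers dosed subjects in escalation cohorts who "withdraw for reasons other than toxicity or are lost to follow-up before completing the safety evaluation period (up to study Day 28) will be replaced". Its second paragraph adds an option: "a replacement subject may be enrolled in the study at the discretion of the Sponsor if one or more enrolled subjects are not fully evaluable". The purposes it names are safety, PK and PD.

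The counting rules are in two places.
- Section 3.1.1: "If a DLT is not seen in the first three subjects, then escalation to the next dose level may occur", and "If more than one DLT occurs in ≤6 subjects in a dose cohort, dose escalation will not occur".
- Section 3.3: "If 1 of the first 3 subjects experiences a DLT during the first 28 days after SBT777101 administration", three more subjects are added, for a total of six. Escalation after 0 of 3, or at most 1 of 6, also requires that "cumulative safety data support tolerability of the dose level as determined by the SMC".

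The definition in section 3.3 begins "A dose-limiting toxicity (DLT) is defined as any treatment-emergent CTCAE" and goes on to require Grade 3 or higher and a relation to study drug, with an exception for certain rapidly reversible Grade 3 infusion reactions.

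**The concern.** Evaluability depends only on why a subject left, not on what was seen before leaving. A subject with a DLT on Day 5 who moves away on Day 20 meets the section 3.3 wording exactly. That subject becomes non-evaluable for the escalation decision and is replaced, while the expansion rule says the same DLT takes the cohort to six. The protocol does not say which sentence prevails.

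The reverse case is less explicit. A subject who leaves on Day 10 because of related Grade 1-2 toxicity has no DLT by definition, did not leave for an unrelated reason, and falls outside mandatory replacement. Nothing takes that subject out of the three or six, although only about a third of the 28-day window was observed (10/28 = 0.36).

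The two sections also word the criterion differently. Section 3.3 asks whether the reason was unrelated to treatment. Section 7.4.3 asks whether it was something other than toxicity, and adds every loss to follow-up, where the reason may be unknown.

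At stake is the escalation decision in a first-in-human study with cohorts of three, where the next planned dose level is three-fold higher.

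**Working it through.** **The plan's own figures.** Three planned levels (section 3.1.3) give 3 × 3 = 9 subjects at minimum and 3 × 6 = 18 in escalation. Three backfill cohorts of up to six add 18, for 36. These match the stated 9, 18 and 36. The protocol gives no target or assumed DLT rate, so the true rate p below is an assumption, with q = 1 − p.

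**The 3+3 rule with no departures.** P(escalate) = q³ + 3pq² × q³. At p = 0.3 this is 0.343 + 0.441 × 0.343 = 0.494.

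**Case A: one DLT in the first three, and that subject then leaves for an unrelated reason.**
- A1, DLT counted: three more subjects are treated and all must be DLT-free, so q³.
- A2, DLT dropped and subject replaced: two DLT-free subjects plus a replacement. Either the replacement is DLT-free (q), or it has a DLT and three more must be clear (p × q³). Total q + pq³.
- A3, subject dropped but the triggered expansion stands: four further subjects with at most one DLT, so q⁴ + 4pq³.

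| p | A1 | A2 | A3 |
|---|---|---|---|
| 0.2 | 0.512 | 0.8 + 0.2 × 0.512 = 0.902 | 0.410 + 0.410 = 0.819 |
| 1/3 | 0.296 | 0.667 + 0.333 × 0.296 = 0.765 | 0.198 + 0.395 = 0.593 |
| 0.5 | 0.125 | 0.5 + 0.5 × 0.125 = 0.563 | 0.0625 + 0.25 = 0.313 |

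**Case B: two DLTs in six, and one of those two subjects leaves for an unrelated reason.** If both count, escalation has probability 0. If one is dropped, the cohort stands at 1 of 5 plus a replacement, and escalates only if the replacement is DLT-free: q = 0.80, 0.67 and 0.50.

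**Case C: two DLT-free completers and one early leaver with related Grade 1-2 toxicity.** Counted as DLT-free, the cohort reads 0 of 3 and the count rule escalates with probability 1. With the leaver replaced, the probability is q + pq³ = 0.902, 0.765 and 0.563.

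**Average over cohorts.** Let w₁ and w₀ be the assumed probabilities of unrelated departure with and without a DLT. The DLT rate among evaluable subjects under the literal rule is p(1 − w₁) / [p(1 − w₁) + (1 − p)(1 − w₀)]. At p = 0.3:

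| w₀ | w₁ | Apparent rate | P(escalate) |
|---|---|---|---|
| 0.10 | 0.10 | 0.27/0.90 = 0.300 | 0.494 |
| 0.10 | 0.25 | 0.225/0.855 = 0.263 | 0.572 |
| 0.10 | 0.50 | 0.15/0.78 = 0.192 | 0.725 |

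The literal rule shifts the average only if leaving is more likely after a DLT.

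All these probabilities are for the count rule alone, before any SMC judgement.

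**The case against.** The best defence is that the counting rules speak of subjects who experience a DLT in the cohort, not of evaluable subjects. On that reading a Day 5 DLT has already triggered expansion, no sentence says a later departure reverses it, and the evaluability sentence is aimed at incomplete observation. This is a fair reading and it is why A3 is shown. It does not remove the conflict: section 3.3 excludes the subject from dose escalation decisions without qualification, and even under A3 the chance of escalating is about double the A1 figure at p = 1/3.

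Safeguards outside the count also exist. The SMC can meet ad hoc after a DLT, must find the cumulative safety data supportive, and has halt rules. The Sponsor may replace a subject who is not fully evaluable. These soften the effect. But SMC judgement is a further condition and does not put a dropped DLT back in the count. The halt rules need a potentially life-threatening related event or similar related SAEs in two or more subjects, so a single Grade 3 DLT may trigger neither. Sponsor replacement is optional, and the text does not say the replaced subject leaves the count. The SMC Charter is not available here and may say more.

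Several stronger readings are tempting but not supported.
- That the rule errs in both directions, so the errors offset. They are opposite misclassifications, one subject wrongly excluded and one wrongly kept, but both favour escalation.
- That the protocol states a low-grade toxicity leaver is DLT-free. It only implies this, and discretionary replacement could cover the case.
- That a DLT subject lost to follow-up is clearly non-evaluable under section 3.3. That section needs an unrelated reason, which may be unknown. Section 7.4.3 replaces the subject but does not say the DLT is discarded.
- That 2 of 6 simply becomes 1 of 6. It does so only with probability 1 − p.
- That escalation is inflated across the trial. With equal departure rates it is not.

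**Conclusion.** The concern holds as a defect of wording with a real consequence in the cohort it touches. Sections 3.3 and 7.4.3 and the synopsis lack an exception for a subject who has already had a DLT, and the literal result contradicts the 1-in-3 expansion rule. The toxicity-leaver gap follows by implication, and the two criteria should be reconciled.

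Conditional on one DLT in the first three and an unrelated departure, dropping and replacing that subject raises the chance of escalating by 0.39, 0.47 and 0.44 at p = 0.2, 1/3 and 0.5. If the expansion stands, the rise is 0.31, 0.30 and 0.19. These sizes rest on assumed DLT rates and on the count rule acting alone. The triggering event should be uncommon within 28 days of a single infusion, and the documents give no departure rates. The harm is that a known DLT may be ignored in a particular cohort, not that the design is biased on average.

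**What to change.** Use one evaluability definition in section 3.3, section 7.4.3 and the synopsis.
1. A dosed subject with a DLT in the 28-day window is always evaluable, counts as a DLT, and is not removed from the count by leaving later.
2. A subject without a DLT who does not complete the window, for whatever reason, is not counted as DLT-free and is replaced for the escalation count. Departures related to toxicity, and losses with an unresolved adverse event, are reviewed by the SMC before the count is closed.

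This takes a few sentences in the next amendment and, occasionally, one more subject in a cohort. It changes how subjects are counted, and no dose or DLT threshold. It also makes the count slightly cautious, because DLT-free leavers are replaced while DLTs always stay. At p = 0.3 with 10% unrelated departure in either case, and assuming departures do not pre-empt DLTs, the apparent rate is 0.3/(0.3 + 0.7 × 0.9) = 0.323 and P(escalate) is 0.449 instead of 0.494. That is a modest price in a first-in-human study.

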1.8. Benefit/Risk Assessment

There has been no prior clinical experience with SBT777101. The objectives for this first in human study are to evaluate the safety, tolerability, PK, PD, and preliminary clinical efficacy of a single dose of SBT777101 in patients with RA, and to inform dose selection for subsequent studies of SBT777101 in RA and other autoimmune diseases.

SBT777101 has not been tested in humans and so the actual risks are unknown. The rationale for evaluating CAR T_{reg} therapy in RA is driven by the potential for this therapy to reduce the signs and symptoms of RA as well as ameliorate disease within the tissue by restoring normal immune balance. Clinical studies and case reports with polyclonal T_{regs} in patients with autoimmune conditions and T_{regs} selected for alloantigen specificity showed that these cells were well tolerated at doses up to and exceeding those proposed in this study. SBT777101 is a regulatory CAR T therapy, not an effector CAR T therapy. As such, the safety profile is expected to reflect more closely that seen in the polyclonal T_{reg} trials rather than that from the CAR T_{eff} trials in patients with oncological diseases.

Overall, the nonclinical data (see Section 1.6) for SBT777101 support this Phase 1 trial in subjects with RA. The potential safety issues associated with administration of study drug are expected to be clinically monitorable and manageable, and measures will be taken to avoid or minimize such toxicities in this trial, as described in Section 7.

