2. OBJECTIVES AND ENDPOINTS

This study will evaluate the safety, tolerability, PK, PD, and preliminary clinical activity of a single intravenous (IV) infusion of SBT777101 in adult subjects with RA that have failed two or more prior b/tsDMARDs. Specific objectives and corresponding endpoints of this study are described below.

Objectives	Endpoints
Primary	
To evaluate and characterize the safety and tolerability of SBT777101	 Incidence, nature, and severity of adverse events Incidence and nature of dose-limiting toxicities (DLTs) Change from baseline in targeted vital signs, clinical laboratory tests and ECG parameters
Exploratory	
To assess and characterize SBT777101 pharmacokinetic profile in peripheral blood and synovium	Peripheral blood CAR transgene PK parameters including, but not limited to, T _{max} , C _{max} , AUC ₀₋₂₈ , and C _{last}

	Presence of SBT777101 in synovial tissue and/or fluid
To assess and characterize SBT777101 mechanism of action and pharmacodynamic parameters in peripheral blood and synovium	 Levels of inflammatory cells and biomarkers in synovial tissue and/or fluid pre-dose and following SBT777101 administration Levels of systemic markers of inflammation in peripheral blood, including but not limited to TNFα, CRP, and IL-6, at baseline and following SBT777101 administration Change from baseline in phenotypic and molecular signatures in T cells and other immune cell subsets in peripheral blood and synovial tissue and/or fluid following SBT777101 administration
To assess immunogenicity of SBT777101	 Presence of circulating anti-drug antibodies (ADA) pre-dose and following SBT777101 administration Detection of cellular immunogenicity pre-dose and following SBT777101 administration
To evaluate the preliminary efficacy of SBT777101	 ACR20, ACR50 and ACR70 response rates following SBT777101 administration DAS28 scores and change from baseline in DAS28 scores following SBT777101 administration

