At the Sponsor's discretion, additional eligible subjects (e.g., those beyond the initial 3 or 6 subjects initially treated as described above) may be enrolled into optional protocol-defined dose level "backfill" cohorts. Each backfill cohort will contain up to six subjects dosed at least 14 days apart. Backfill cohorts will not be opened until the dose escalation cohort at that dose level has been completed. Doses will not exceed the last cleared dose from the initial dose escalation cohorts.

Additional subjects may be enrolled at the Sponsor's discretion under the following conditions:

[figure not shown]

- Inability to manufacture the required dose of SBT777101 for any given subject, wherein the number of CAR positive T_{reg} cells is in the final drug product is insufficient for the assigned dose level. In this case, the subject may be enrolled into a backfill cohort at the highest possible cleared dose level (e.g., a subject intended for dose level 2 may be enrolled in dose level 1 backfill).
- Evaluation of PK, PD and biomarker data from a dose cohort indicates that additional data may better aid interpretation of preliminary PK and PD data and to guide future dose selection. Subjects may be added provided that the SMC does not indicate that doing so will present additional safety risks.

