9.4. Endpoints

9.4.1. Primary Endpoint

To evaluate and characterize the safety and tolerability of SBT777101:

- Incidence, nature and severity of AEs
- Incidence and nature of DLTs
- Changes from baseline in clinical laboratory tests, 12-lead ECG parameters and targeted vital signs

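### Minor: Section 3.3 can name the prior dose level the MTD on 0 DLTs in only 3 subjects, and nothing in the protocol requires more subjects first

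*Protocol*

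**What the plan says.** The design is a 3+3 with three planned dose levels. Section 3.1.1 states: "If a DLT is not seen in the first three subjects, then escalation to the next dose level may occur". Section 3.3 clears a level on 0 DLTs in 3 or at most 1 in 6, provided that "cumulative safety data support tolerability of the dose level as determined by the SMC". If two or more subjects in a cohort have a DLT, or the overall toxicity is judged unacceptable, escalation stops and "either the prior dose level will be considered the maximum tolerated dose (MTD) or an intermediate dose level will be evaluated".

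The routes to more than three subjects at a level are:

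- **Mandatory expansion to six** follows only 1 DLT in the first 3 (Sections 3.1.1 and 3.3).
- **SMC expansion from three to six** is permitted when events suggest a significant safety risk or a pattern of toxicity (Section 3.3).
- **Backfill** is at the sponsor's discretion. Additional subjects "may be enrolled into optional protocol-defined dose level" cohorts of up to six (Section 3.1.1), and Section 7.4.3 adds: "Subjects in backfill cohorts that withdraw from the study will not be replaced".
- **Replacement** of non-evaluable escalation subjects (Sections 3.3 and 7.4.3) restores the intended count but does not raise it.

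MTD is not a listed objective or endpoint. The primary objective is "To evaluate and characterize the safety and tolerability of SBT777101" (Section 2), and the related endpoint is "Incidence and nature of DLTs" (Section 9.4.1).

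**The concern.** A level that passes cleanly on three subjects can become the MTD because the level above it failed, with no further subject treated at the dose that receives the name. Nothing in Section 3.3 separates a level cleared for escalation from a level supported well enough to be called the MTD.

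What is at stake is how the result is read later. Section 1.8 says the study is "to inform dose selection for subsequent studies of SBT777101 in RA and other autoimmune diseases". A team designing the next trial may take the term MTD to mean that the dose was tested further than three subjects allow.

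**Working it through.** **Planned numbers.** Three levels of three give 3 x 3 = 9, the stated minimum treated. Three levels of six give 3 x 6 = 18, the escalation ceiling in Section 9.1. Optional backfill adds 3 x 6 = 18, for a total of 36. All match the protocol. The minimum of 9 confirms that running every level on three subjects is a planned outcome.

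**What the counts show about the DLT rate** (one-sided 95% Clopper-Pearson upper bounds)

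- 0/3: 1 - 0.05^(1/3) = 0.632
- 0/6: 1 - 0.05^(1/6) = 0.393
- 1/6: the p that solves (1-p)^6 + 6p(1-p)^5 = 0.05, which is 0.582

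**What three more subjects would add.** Let p be the true DLT rate and q = 1 - p. The protocol gives no DLT rates, so the values of p are assumptions.

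- Current rule, chance that a level qualifies: q^3 + 3pq^2 x q^3
- Six subjects with at most 1 DLT: q^3 x P(at most 1 DLT in the next 3) + 3pq^2 x q^3
- After 0/3, chance that the next three show 2 or more DLTs: 3p^2 q + p^3

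Example at p = 0.3: the current rule gives 0.343 + 0.441 x 0.343 = 0.494. Requiring six gives 0.343 x 0.784 + 0.441 x 0.343 = 0.420.

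| Assumed p | Qualifies, current rule | Qualifies, six required | 2+ DLTs in next 3 after 0/3 |
|---|---|---|---|
| 0.1 | 0.906 | 0.886 | 0.028 |
| 0.3 | 0.494 | 0.420 | 0.216 |
| 0.4 | 0.309 | 0.233 | 0.352 |
| 0.5 | 0.172 | 0.109 | 0.500 |

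So after 0/3 the label would survive the extra three subjects 97%, 78%, 65% and 50% of the time.

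**How often a level clears on three subjects.** Among levels that clear on DLT counts, the share that do so on 0/3 is q^3/(q^3 + 3pq^2 x q^3) = 1/(1 + 3pq^2). It is lowest at p = 1/3, where it equals 1/(1 + 12/27) = 0.692. This ignores signal-triggered expansion and backfill.

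**How often an MTD would be named on 0/3.** The next level must also fail, so the answer depends on the assumed rates at all three levels. The figures below assume that the MTD branch is always chosen over the intermediate dose.

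- Rates of 5/15/40%, 10/25/50% and 15/30/50%: a prior level is named in 73%, 81% and 75% of trials, and named on 0/3 in 57%, 61% and 54%.
- Rates of 2/5/10%: the levels clear with probability 0.995, 0.973 and 0.906. A prior level is named with probability 0.995 x 0.027 + 0.995 x 0.973 x 0.094 = about 0.12. It is named on 0/3 with probability 0.941 x 0.027 + 0.995 x 0.857 x 0.094 = about 0.105.

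**The case against.** **A reader might infer that 0/3 is weaker evidence than the protocol's six-subject clearance of at most 1 in 6.** The documents do not support that. On counts alone, a level reaches six only after 1 DLT in 3, so a six-subject clearance is then always exactly 1/6. The upper bounds are close (63% against 58%), and by likelihood 0/3 is the better result. For a true rate of 40% against 10%, the likelihood ratio is 0.216/0.729 = 0.30 after 0/3 and 0.187/0.354 = 0.53 after 1/6. At a true rate of 30%, a dose passes 0/3 34% of the time and at most 1/6 42% of the time. The case therefore rests on the added information from three more subjects, for which the fair contrast is 0/3 with 0/6.

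**A reader might also take the 69% as the chance of an MTD named on 0/3.** It is only the minimum share of count-cleared levels that clear that way. Section 1.8 expects a safety profile close to that of polyclonal Treg trials, and low rates make the event uncommon.

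**The label does little within the trial.** It is not an objective or endpoint, and backfill dosing is capped by the last cleared dose. Section 9.5 presents results by dose level, so the number treated would be visible. Subject protection is unchanged by the label. This stands, and it keeps the point minor.

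**Other routes may avoid the outcome.** The intermediate dose is an explicit alternative, the SMC keeps reviewing safety, and one stated purpose of backfill is to guide future dose selection. The lack of backfill replacement matters little: with a full backfill, 3 + 6 = 9, and four subjects would have to be non-evaluable before the count fell below six. These routes are real, but none is required before the label is used. Sections 3.3 and 3.4 also refer to an SMC Charter that is not shown, so a minimum set there cannot be excluded.

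**Conclusion.** The point holds as a minor one. Section 3.3 permits, but does not compel, an MTD named on three DLT-free subjects. This is a rule fixed in the protocol, not a detail left to the SAP. Asking for six subjects lowers the chance that a level qualifies by about 7 to 8 percentage points at assumed true DLT rates of 30% and 40%, and by about 2 points at 10%. Those rates are assumptions. The text does not show that subjects are at greater risk, that the primary objective is compromised, or that most MTDs would rest on 0/3 irrespective of the true rates.

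**What to change.** Amend Section 3.3 as follows:

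- Use 'MTD' only for a level with at least six DLT-evaluable subjects and an observed DLT proportion of no more than 1 in 6. That means at most 1 DLT in 6 to 11 subjects and at most 2 in 12.
- Count backfill subjects at that dose if they were followed for DLTs over 28 days.
- Otherwise report 'highest cleared dose; MTD not established'.
- With either label, state the number of evaluable subjects and of DLTs at that level.

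The change requires no added subjects; its cost is then a weaker label. If the sponsor chooses to earn the MTD label, it takes up to three more subjects. With three planned levels and no replacements, that stays within the escalation ceiling of 18. The time is about 56 days from first dosing (2 x 14 days of spacing plus 28 days of follow-up). To this add about 8 to 10 weeks for screening (about 2 weeks) and pre-treatment with apheresis and manufacture (6 to 8 weeks), unless those subjects were already prepared at risk, as Section 3.1.1 permits for screening and apheresis.
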